7.4 Disposition of Subjects

A subject disposition summary presented by treatment group and overall will be provided. The categories will include all subjects who were not treated, subjects who discontinued from the study early categorized by reason, subjects who completed the study, subjects who discontinued treatment early categorized by reason, and subjects who completed treatment. Post-randomization discontinuation reasons include pretreatment event or adverse event, significant protocol deviation, lost to follow-up, voluntary withdrawal, study termination, pregnancy, non-compliance with study drug, and other. A listing will be presented to describe study treatment, date of first dose, date of last dose, date of completion or early withdrawal, and the reason for early discontinuation.

A summary of screening failures and listings of inclusion/exclusion criteria responses for subjects with violations will also be provided.

7.5 Demographic and Baseline Characteristics

Demographic and baseline characteristics including sex, age, race, ethnicity, height, weight, body mass index (BMI), smoking habit, female reproductive status, menstruation condition, and sexual dysfunction status. The demographic and baseline characteristics summary will be based on all randomized subjects. Summaries based on the full analysis set will also be created.

Baseline values for efficacy parameters (CSFQ-14) will also be presented for each treatment group and overall based on all randomized subjects.

Height and weight values will be presented in metric units (cm and kg). BMI is calculated as [weight (kg)/height (m)²], using the weight collected at the first screening visit (Visit 1) in the study.

Race is classified into Caucasian, Black, Asian, American Indian or Alaska Native, Native Hawaiian or Other Pacific Islander. In addition, ethnicity (Hispanic or Latino) is also captured.

Female reproductive status is classified into four categories: postmenopausal, surgically sterile, female of childbearing potential and NA/subject is male. Menstruation condition includes duration of menstruation and duration of menstrual cycle.

For continuous variables, the number of non-missing values and the mean, median, SD, minimum and maximum will be tabulated by treatment group and overall. For the categorical variables, the count and percentages of each possible value will be tabulated by treatment group and overall.

For continuous variables, comparability of treatment groups will be assessed using an analysis of variance (ANOVA) with treatment and center as fixed factors. For discrete variables, comparability will be assessed using the Cochran-Mantel-Haenszel general association test, stratified by center. P-values will be displayed as descriptive statistics of comparability.

All individual demographic and baseline data will be listed by treatment, study center and subject number.

7.6 Medical History and Concurrent Medical Conditions

Medical history refers to the significant conditions/diseases that stopped at or prior to Screening (time of informed consent). Concurrent medical conditions are those significant ongoing conditions/diseases present at Screening (time of informed consent).

Medical history and concurrent medical conditions will be coded using the Medical Dictionary for Regulatory Activities (MedDRA) version 13.0 and will be summarized by treatment group and overall using System Organ Class (SOC) and MedDRA preferred term. The table will include number and percentages of subjects with system organ class terms sorted alphabetically and preferred terms sorted by decreasing frequency based on the total number of subjects. A subject will only be counted once within a particular class even if he/she has multiple conditions/symptoms. Summaries will be based on all randomized subjects.

All medical history and concurrent medical condition data will be listed by treatment, study center and subject number. The listing will contain subject identifier, whether there was any significant medical history or concurrent condition, including system organ class, preferred term and details of the medical history or condition.

7.7 Medication History and Concomitant Medications

The medication history and concomitant medications are defined as follows:

- Medication history refers to the medication that the study subjects stopped taking at or within 90 days prior to the Screening Visit (ie, stop date \leq first screening visit date).
- Concomitant medication is defined as medication that the study subjects continued taking or took from Screening through end of study:
 - Concomitant medication that started and stopped prior to baseline (ie, stop date $>$ first screening visit date, and stop date \leq first dose date).
 - Concomitant medication that started prior to and was ongoing at baseline (ie, start date $<$ first dose date, and stop date $>$ first dose date).
 - Concomitant medication that started after baseline but before or at last dose (ie, start date \geq first dose date, and start date \leq last dose date).
 - Concomitant medication taken during the study (ie, start date \leq last dose date, and stop date $>$ first dose date).

- If start date and stop date are missing, medication will be assumed to occur both prior and concomitantly.

Medication history and concomitant medications will be coded using the 01MAR2016E version of the World Health Organization (WHO) Drug Dictionary and summarized by giving the number and percentage of subjects by preferred term, with preferred terms sorted by decreasing frequency based on the total number of subjects. If a subject reports taking 2 drugs belonging to the same preferred term, he/she will only be counted once within that preferred term. Summaries of medication history and concomitant medication will be based on all randomized subjects.

All prior and concomitant medications will be listed by treatment, study center and subject number. The listings will contain subject identifier, WHO Drug preferred term and reported term, dose, unit, route, frequency, the indication for which the medication was being taken, start date, stop date, and whether the medication was ongoing.

7.8 Study Drug Exposure and Compliance

The summary of study drug exposure and compliance will be based on the safety set.

Duration of exposure to double-blind study medication is defined as (date of last dose – date of first dose +1). Treatment duration will be summarized by duration category in days (1 to 6 days, 7 to 13 days, 14 to 20 days, 21 to 27 days, 28 to 34 days, and ≥ 35 days) and the number of subjects in each duration category by treatment group. Treatment duration (weeks) will also be summarized using descriptive statistics (n, mean, SD, median, minimum, and maximum).

Percent of study drug compliance is defined as $\{(number\ of\ capsules\ dispensed - number\ of\ capsules\ returned) / (date\ of\ last\ dose - date\ of\ first\ dose + 1)\} \times 100\%$. If a value for the number of returned capsules is missing or the return date is missing, then 100% compliance will be assigned for each day up to the number of capsules dispensed or up to the date of return whichever is earlier.

For each treatment group, study medication compliance will be summarized by compliance category (<80%, 80 to 120%, and $\geq 120\%$) and the number of subjects in each compliance category. Study medication compliance will also be summarized as a continuous variable using descriptive statistics (n, mean, SD, median, minimum, and maximum) for each treatment group.

All study drug administration and accountability data will be listed by treatment, study site, and subject number. The following variables will be listed: subject identifier, visit number, first and last dose dates, medication identification number, date dispensed and returned, number of capsules dispensed and returned, and percent compliance.

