7. Noncompliance with study drug. This includes subjects who did not take the study drug for ≥ 4 consecutive days and/or are $<70\%$ compliant between visits.
8. Other.

Note: The specific reasons should be recorded in the "specify" field of the eCRF.

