If the study drug is not taken or is not taken correctly, the study site will be notified through the dashboard as well as by email or short message service (SMS) messaging. Study sites will be able to intervene with the subject directly through the dashboard if the study drug is not taken or not taken correctly. In addition, subjects will receive an automated message to their device reminding them to take their study drug, or if there is a low battery. The device will ring if subjects are late in taking their study drug. Subjects will provide written consent to be contacted via SMS messaging

in accordance with their use of the AiCure platform, at the clinical site when agreeing to participate in the study.

Subjects will be trained on how to use the application and will participate in a practice session at the Baseline Visit. During the practice session, subjects will be requested to take small practice pills to demonstrate that they are able to use the application. The practice pills are a commercially available product (ie, small white or colored candies) and will be provided by AiCure.

If a subject is persistently noncompliant with the study drug (eg, ≥ 4 consecutive doses missed and/or $<70\%$ compliant between visits), the medical monitor should be consulted to discuss whether it may be appropriate to withdraw the subject from the study. All subjects should be re instructed about the dosing requirements during study contacts. The authorized study personnel conducting the re-education must document the process in the subject source records.

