13.0 STATISTICAL METHODS

13.1 Statistical and Analytical Plans

A statistical analysis plan will be prepared and finalized prior to unblinding of subject treatment assignments. This document will provide further details regarding the definition of analysis variables and analysis methodology to address all study objectives.

A blinded data review will be conducted prior to unblinding of subject treatment assignments. This review will assess the accuracy and completeness of the study database, subject evaluability, and appropriateness of the planned statistical methods.

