13.1.1 Analysis Sets

The full analysis set (FAS) will include all subjects who were randomized, received at least 1 dose of double-blind study drug, and have at least 1 valid postbaseline value for assessment of the primary efficacy endpoint. In FAS efficacy summaries, subjects will be analyzed by the treatment to which they were randomized.

To adjust for treatment noncompliance, one or more modified FAS populations will be defined.

The per-protocol analysis set (PPS) will include all subjects in the FAS who had no major protocol violations. Subjects to be excluded from the PPS, whether due to protocol violations or noncompliance to the dosing schedule, will be identified in the minutes of the subject evaluability assessment performed prior to unblinding.

The safety analysis set will include all subjects who were randomized and received at least 1 dose of double-blind study drug. In safety summaries, subjects will be analyzed according to the treatment they received. In the event that a subject receives more than 1 treatment, the actual treatment will be defined as the one that is used most frequently. If the 2 most common treatments are used with equal frequency, then the randomized treatment will be used as the actual treatment.

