7.2 Major Protocol Violations

All subjects with major protocol violations will be identified in the minutes of the subject evaluability assessment performed prior to unblinding, and will be listed by study center and subject number.

Subjects with the following major protocol violations will be excluded from the per protocol set (PPS):

- No evaluable baseline CSFQ-14 assessment.
- No evaluable post-baseline assessment of CSFQ-14.
- Low study drug compliance (<70%) or missed study drug for 4 consecutive days.
- Double-blind study medication exposure less than 7 days (last dose date – first dose date +1 <7).
- Subjects switch treatment during study.

Other major protocol violations will be identified by the study team prior to unblinding.

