7.3 Analysis Sets

The safety set will include all subjects who were randomized and received at least 1 dose of double-blind study medication. In safety summaries, subjects will be analyzed according to the treatment they received. In the event that a subject receives more than 1 treatment, the actual treatment will be defined as the 1 that is used most frequently. If the 2 most common treatments are used with equal frequency, then the randomized treatment will be used as the actual treatment.

The full analysis set (FAS) will include all subjects who were randomized, received at least 1 dose of study drug, and had at least 1 valid post-baseline value for assessment of primary efficacy. In FAS efficacy summaries, subjects will be analyzed by the treatment to which they were randomized.

To adjust for treatment noncompliance, two modified FAS populations, mFAS1 and mFAS2, will be defined based on the PK data. The mFAS1 excludes subjects in the vortioxetine treatment

CONFIDENTIAL

arm who had drug concentration below the limit of quantification at all study visits where PK is collected, while the mFAS2 excludes subjects in the vortioxetine treatment arm who had drug concentration below the limit of quantification at any study visit where PK is collected. The PPS will include all FAS subjects who had no major protocol violations. If more than 5% of the total subjects in the FAS have major protocol violations, analyses based on the PPS will be performed for the primary efficacy variable only.

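### SAP 7.8 scores a missing capsule return as full compliance and can override a recorded count; SAP 7.2 gives neither source nor period for the <70% per-protocol criterion that may rest on it

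*SAP*

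**What the plan says.** SAP 7.8 holds the SAP's only definition of percent compliance: capsules dispensed minus capsules returned, divided by the days from first to last dose. Its missing-data rule reads "If a value for the number of returned capsules is missing or the return date is missing, then 100% compliance will be assigned" and continues "for each day up to the number of capsules dispensed or up to the date of return whichever is earlier". The result is tabulated on the safety set as below 80%, 80 to 120%, and 120% or more.

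SAP 7.2 lists as a major violation that excludes a subject from the PPS: "Low study drug compliance (<70%) or missed study drug for 4 consecutive days". It does not refer to 7.8 and gives no data source or scoring period. SAP 7.3 adds: "If more than 5% of the total subjects in the FAS have major protocol violations, analyses based on the PPS will be performed". That repeat is confined to the primary variable.

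The protocol uses the same pair of limits, but per interval. Section 7.4 defines noncompliance as a discontinuation category: "This includes subjects who did not take the study drug for" four or more consecutive days, and/or who fall below 70% between visits. Under Section 9.2, for such subjects "the medical monitor should be consulted to discuss whether it may be appropriate to withdraw the subject from the study".

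Protocol 9.2 also describes a smartphone app that records each dose and allows later manual entry. SAP 7.2, 7.3 and 7.8 do not mention it.

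**The concern.** There are three weaknesses.

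- **Favourable imputation.** An unknown number of leftover capsules becomes perfect intake. The error runs in one direction only, so the compliance table can only be too high.
- **Override of known data.** The rule applies if the count or the date is missing. With the count recorded and only the date blank, the formula can still be computed, because it uses counts and dose dates. The rule nevertheless replaces it with 100%.
- **An undefined link to the PPS.** A programmer who needs a percentage for the <70% criterion finds only 7.8. If that figure is used, the credit can lift an intermittent taker over 70%. The separate 4-consecutive-day criterion does not settle this. A subject who misses 3 of 7 days can have no gap longer than one day, and a capsule count cannot show whether missed days were consecutive.

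At stake are the compliance table, the count of violators compared with the 5% trigger, and the membership of the PPS if that analysis is run.

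**Working it through.** **The plan's own figure.** The documents state no number for the compliance rule. The nearest figure is the power statement (SAP 6.0), with SD 8.5, 88 per arm, difference 4.0 and 2-sided 0.025. The standard error is 8.5 × √(2/88) = 1.28. Noncentral t power is 80.4%, and Holm simulation gives 85.3% per dose. Both agree with the stated values, and neither is affected by this point. The SE is used below.

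**Inputs.** Five weekly bottles of 10 capsules, 7 doses plus 3 spare (Protocol 8.1.1); 35 dosing days; the 7.8 rule; the 70% limit (SAP 7.2). Assumed: equal 7-day intervals, and a subject who takes 4 of 7 capsules each week, true compliance 20/35 = 57%.

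**Whole-period scoring from 7.8; k counts missing, return dates known, 7 days credited each.** Score = [4(5 − k) + 7k]/35.

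| k | Score | <70% criterion |
|---|---|---|
| 0 | 20/35 = 57% | excluded |
| 1 | 23/35 = 66% | excluded |
| 2 | 26/35 = 74% | kept |
| 3 | 29/35 = 83% | kept; tabulated as 80 to 120% |

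**Random misses (assumption: independent, daily probability of taking 4/7).** Passing needs at least 25 credited days of 35 (0.70 × 35 = 24.5).

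- k = 0: P(Bin(35) ≥ 25) = 6%
- k = 1: P(Bin(28) ≥ 18) = 29%
- k = 2: P(Bin(21) ≥ 11) = 75%

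If true dosing on all 35 days is also checked for a 4-day gap, with the missing bottles placed last, these become 6%, 22% and 45%.

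**Between-visit scoring, as in Protocol 7.4 and 9.2.** Each counted interval must itself reach 70%, that is 5 of 7 or more. The 4-of-7 subject scores 57% in every counted interval and is excluded with one, two, three or four missing returns. Under random misses, P(Bin(7) ≥ 5) = 0.359. With one missing return, 0.359⁴ = 1.7%. With two, 0.359³ = 4.6%.

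**Return date blank.** The return-date cap then drops out and only the 10 capsules dispensed remain as a limit. Read literally, two such intervals give (4 × 3 + 10 × 2)/35 = 32/35 = 91%, and one gives (4 × 4 + 10)/35 = 26/35 = 74%, even if the counts are on file. This reading is uncertain, because it credits 10 days to a 7-day interval.

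**Trigger.** With a FAS of 352, 5% is 17.6, so 18 violators are needed. Illustration: 20 violators (20/352 = 5.7%) with 3 wrongly kept become 17 (4.8%), and the PPS analysis is not run.

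**Effect on the PPS estimate (assumption).** Suppose 1% to 5% of the paroxetine arm are wrongly kept and lose a quarter to half of a 4.0-point effect. The shift is then 4.0 × 0.01 × 0.25 = 0.01 to 4.0 × 0.05 × 0.50 = 0.10 points, or 0.01 to 0.08 SE.

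**The case against.** The strongest reply is that SAP 7.8 was written for a descriptive table. Its cut-points are 80% and 120%; it mentions neither 70% nor the PPS, and SAP 7.2 does not cite it. The 70% and 4-day pair in 7.2 mirrors the protocol's noncompliance rule, which works between visits. On that basis the worked example is excluded as soon as one interval is counted. This stands, and it is why the kept/excluded figures are conditional. It does not remove the gap, because 7.2 says neither which score nor which period applies.

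Existing controls also count. Subjects bring containers to every visit (Protocol 9.2), and sites must investigate and document unreturned drug (Protocol 8.6). PPS exclusions, "whether due to protocol violations or noncompliance to the dosing schedule, will be identified in the minutes of the subject evaluability assessment", are settled before unblinding. Of the blinded data review, Protocol 13.1 says: "This review will assess the accuracy and completeness of the study database, subject evaluability, and appropriateness of the planned statistical methods". SAP 7.2 lets the team add other major violations, and SAP 7.8 lists dispensed and returned counts. These controls make a wrong inclusion less likely. None supplies a score to replace the credited one.

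A reader might infer that one missing return gives a subject 100% overall, or that 29% and 75% are the expected leak. The documents support neither. The credit covers only the days of the affected interval, and the percentages assume whole-period scoring, random misses and missing returns that have already occurred.

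**Conclusion.** The point holds and is minor. Two parts need no further assumption about 7.2: the rule scores missing returns favourably, which biases the compliance table upward, and as worded it discards a recorded count when only the date is blank.

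The PPS consequence is conditional. With whole-period scoring from 7.8 and return dates known, two missing counts keep a 57% taker. With between-visit scoring the chance of passing under random misses is about 2% with one missing return and 5% with two. The blank-date score of up to 91% rests on a literal but uncertain reading of the cap.

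A reader might conclude that the trial's main result is at risk. It is not: the primary analysis uses the FAS, which has no compliance criterion. What can change is the compliance summary, whether the >5% trigger is met, and who is in a conditional supportive analysis. Under the stated assumptions that analysis would shift by no more than 0.10 points against an SE of 1.28. The documents give no rate of missing returns, so every figure here is a scenario.

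**What to change.** Before unblinding:

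- **SAP 7.8.** Use the returned count whenever it is recorded, even if the return date is missing. When the count is missing, do not assign 100%. Use the app's dose record for that interval, with manual entries flagged, or the site's accountability result. If neither exists, compute compliance over the intervals with data and refer the subject to the blinded evaluability review.
- **SAP 7.2.** State the source and the scoring period for <70%, and reconcile the period with the between-visit wording of Protocol 7.4 and 9.2. Name the app's dated dose record as the source for the 4-consecutive-day criterion. The dose dates taken at the three PK visits (Protocol 9.1.16.1) can serve only as a cross-check, since each visit captures just the last prior dose and the dose taken at the site.
- **Listing.** Keep the current capsule-count figure as a sensitivity listing.

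The cost is a few sentences of SAP text and one merge of app data that the trial already collects. The app may under-record when the device is absent or fails, which is the reason for the flag and the listing. Scoring only the intervals with data is itself an assumption, which is why those subjects go to blinded review. The reported compliance rate may be lower.

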7.9 Efficacy Analysis

The analyses and summaries will be based on the FAS.

7.9.1 Overview of Primary, Secondary and Additional Variables

The primary, secondary and additional variables for this study are presented in [Table 7](#).

Table 7.b Primary, Secondary and Additional Variables

Parameter	Description	Variable Type (a)
CSFQ-14	CSFQ-14 total score	1
PGI-I	PGI improvement	2
Sexual dysfunction (abnormal) assessed by CSFQ-14	CSFQ-14 total score ≤ 47 for men or ≤ 41 for women	3
Time to sexual dysfunction	Time to CSFQ-14 total score ≤ 47 for men or ≤ 41 for women	4
C-SSRS	Columbia-Suicide Severity Rating Scale	2
CSFQ _i	CSFQ-14 single item i	2
CSFQ 5-dimensions: Pleasure	CSFQ-14 item 1	2
CSFQ 5-dimensions: Desire/Frequency	Sum of CSFQ-14 items 2 and 3	1
CSFQ 5-dimensions: Desire/Interest	Sum of CSFQ-14 items 4, 5, and 6	1
CSFQ 5-dimensions: Arousal/Erection	Sum of CSFQ-14 items 7, 8, and 9	1
CSFQ 5-dimensions: Orgasm/Ejaculation	Sum of CSFQ-14 items 11, 12, and 13	1
CSFQ 3-phases: Desire	Sum of CSFQ-14 items 2, 3, 4, 5, and 6	1
CSFQ 3-phases: Arousal	Sum of CSFQ-14 items 7, 8, and 9	1
CSFQ 3-phases: Orgasm/Completion	Sum of CSFQ-14 items 11, 12, and 13	1
Δ CSFQ ≤ -3	CSFQ negative response (≥ 3 decrease from baseline)	3
Time to Δ CSFQ ≤ -3	Time to CSFQ negative response	4

(a) 1 = continuous; 2 = categorical; 3 = binary; 4 = time to event.

